#### **6.1.1 Screening Visit (28 days before start of treatment)**

During the Screening period and before any trial-related investigations and assessments are started, subjects will be asked to sign the informed consent form (ICF). The Screening procedures and Baseline assessments will be completed within 28 days of signing the ICF before first trial treatment.

The subjects' information that will be documented during Screening includes the demographic information (date of birth, sex, race and ethnicity) and the complete medical history (oncology history, previous and ongoing medications, prior surgery, radiation and medication therapies, and baseline medical condition etc). The AE reporting period for safety surveillance and a concomitant medication recording period begins when the subject first signs an informed consent.

During Screening, subjects will undergo a complete physical examination, vital signs, recording height and body weight, 12-lead ECG, and a determination of the ECOG performance status.

During Screening, pathology reports will be reviewed to confirm diagnosis.

The Screening laboratory examination includes hematology, coagulation, serum chemistry, anti-AChR autoantibody, anti-MuSK autoantibody, immunoglobulin, urinalysis, troponin, B cell count, neutrophil count, lymphocyte count, Cardiac ultrasonography, total T3, free T3, free T4 and TSH will also be assessed at Screening for all subjects. Viral tests for HBV, HCV and HIV should be performed at Screening.

During Screening, a serum beta-human chorionic gonadotropin pregnancy test will be performed for females of childbearing potential. Females who are postmenopausal or who have undergone hysterectomy or bilateral oophorectomy are exempt from pregnancy testing. If necessary to confirm postmenopausal status, FSH will be drawn at Screening.

During Screening, the tumor evaluation will be performed using CT scan or MRI or any other established methods. A brain CT/MRI scan is required at Screening if not performed within 42 days prior to first trial treatment.

Failure to establish subject eligibility due to laboratory parameters is allowed to be re-tested following consultation with the Medical Monitor.

#### **6.1.2 Treatment Phase**

The Treatment period begins on Cycle 1 Day 1 with the first administration of KN046 and will continue until 2 years have passed or until confirmed disease progression per RECIST 1.1, significant clinical deterioration (clinical progression), unacceptable toxicity, or any criterion for withdrawal from the investigational medicinal product. A subject may remain on KN046 beyond disease progression per RECIST 1.1 if their ECOG performance status remains stable, no new symptoms or worsening of existing symptoms and if in the opinion of the investigator the subject will benefit from continued treatment. For subjects that continue KN046 treatment beyond progression, treatment should be stopped immediately if the subject no longer tolerates KN046 or if therapeutic failure occurs.

Subjects will be asked to visit the study site every 2 weeks during the Treatment Period. A time window of up to 3 days before or after the scheduled visit day (+/-3 days) will be permitted for all study procedures except for body weight, which should be measured on the day prior to, or the day of, administration of KN046. In addition, the tumor evaluation has a tumor assessment

window of up to 7 days before or after the scheduled visit day (+/- 7 days) throughout the Treatment phase.

#### **6.1.2.1 Day 1 of each Cycle (unless otherwise noted in the SOA)**

- Concomitant medications and procedures
- Adverse Event Assessment
- Full physical exam
- Body Weight
- Tumor Imaging (if applicable)
- Vital Signs
- 12-lead ECG (if clinically indicated)
- ECOG Performance Status
- CBC, metabolic panel, CPK, troponin
- Coagulation tests (if clinically indicated)
- Urinalysis (as defined in SOA)
- T3, FT3, FT4, TSH (as defined in SOA)
- CRP, IL-6 (as clinically indicated)
- Anti-AChR Autoantibody, Anti-MuSK autoantibody (as clinically indicated)
- For C2D1 and C3D1 only: Cardiac Ultrasonography
- Tumor Imaging (to occur every 8 weeks)
- Brain CT/MRI (as clinically indicated)

#### **6.1.2.2 Day 15 of each Cycle**

- Concomitant medications and procedures
- Adverse Event Assessment
- Full physical exam
- Body Weight
- Tumor Imaging (if applicable)
- Vital Signs
- ECOG Performance Status
- CBC, metabolic panel, CPK, troponin
- Coagulation tests (if clinically indicated)
- Urinalysis (as defined in SOA)
- T3, FT3, FT4, TSH (as defined in SOA)
- CRP, IL-6 (as clinically indicated)
- Brain CT/MRI (as clinically indicated)
- For C2D15 only: Cardiac Ultrasonography

#### **6.1.3 End of Treatment**

- Concomitant medications and procedures
- Adverse Event Assessment
- Physical exam
- Body Weight
- Vital Signs

- 12-lead ECG
- ECOG Performance Status
- CBC, metabolic panel
- Urinalysis (as defined in SOA)
- T3, FT3, FT4, TSH (as defined in SOA)
- Tumor Imaging

#### **6.1.4 Safety Follow Up Phase**

- Concomitant medications and procedures
- New anti-cancer therapy Assessment
- Adverse Event assessment
- Full physical exam
- Body Weight
- Vital Signs
- ECOG Performance Status
- CBC, metabolic panel
- Coagulation tests (if clinically indicated)
- Urinalysis (as defined in SOA)
- T3, FT3, FT4, TSH (as defined in SOA)
- Tumor Imaging (to occur every 8 weeks)

#### **6.1.5 Survival Follow Up Phase**

- Concomitant medications and procedures
- New anti-cancer therapy Assessment
- Adverse Event assessment
- Full physical exam
- Body Weight
- Vital Signs
- ECOG Performance Status
- CBC, metabolic panel
- Coagulation tests (if clinically indicated)
- Urinalysis (as defined in SOA)
- T3, FT3, FT4, TSH (as defined in SOA)
- Tumor Imaging (to occur every 8 weeks)

### **7. Study Intervention**

#### **7.1 Study Intervention/Device Description**

KN046 is the investigational medicinal product of this study.

KN046 is a sterile, clear and colorless to light yellow solution intended for IV administration. It is presented as a 40 mg/1.6 mL/vial in a single use glass vial closed with a rubber stopper and sealed with an aluminum polypropylene flip-off seal.

## 7.2 Dilution and Dosing

Subjects in this trial will receive IV infusion of KN046 over at least 90 minutes (90~120 minutes) once every 2 weeks.

The volume of KN046 solution will be calculated based on the body weight of the subject determined the day prior to, or on the day of each drug administration. For a 70 kg subject who is enrolled and planned to receive 5 mg/kg treatment, the dose of KN046 is 350 mg, and the volume of solution is  $350 \text{ mg} / 40 \text{ mg} \times 1.6 \text{ mL} = 14 \text{ mL}$ . The dilution needs to be done aseptically by transferring 14 mL of 40 mg/ 1.6 mL KN046 from 9 vials into 186 mL of sterile 5% dextrose in water to have a final concentration of KN046 for infusion at 1~5 mg/mL. The diluted KN046 solution should be mixed gently and thoroughly before application by intravenous infusion, with an adequate normal saline flush at the end of the infusion.

Visual inspection of the diluted solution and the vials for particulate matter and discoloration prior to infusion will be conducted. The infusion duration should be no less than 90 minutes. KN046 should be administered under the supervision of physician or other study personnel experienced in the use of IV agents. Do not administer study drug as an IV push or bolus injection.

For the detailed process of the dilution and infusion, please refer to the Pharmacy Manual.

Every subject will receive KN046 at protocol scheduled dose and regimen until confirmed disease progression per RECIST 1.1 criteria, significant clinical deterioration (clinical progression), unacceptable toxicity, start of new anti-cancer therapy, withdrawal of informed consent, or until protocol-defined criteria for withdrawal from KN046 or the study are met. Dose modifications of KN046 is discussed in Section 7.3.

After initial determination of disease progression per RECIST 1.1, if patient is clinically stable, a subsequent assessment should be performed preferably 4~8 weeks (but not later) after initial documentation of progressive disease (PD) to determine whether there has been a decrease in the tumor size, or continued PD (Confirmed Progression).

The decision to continue treatment beyond progression should be discussed with the Principal Investigator and Treating physician and documented in the study records.

## 7.3 Dose modifications

KN046 will be withheld for  $\geq$  Grade 3 drug-related toxicity, including laboratory abnormalities with the exception of laboratory abnormalities that are not clinically significant or that do not meet the criteria of adverse event, and severe or life-threatening AEs (i.e. anemia grade 3, lymphocytopenia grade 3-4, hypercholesterolemia grade 3-4, hypertriglyceridemia grade 3-4).

If a dose of KN046 is withheld due to toxicity, subjects may resume dosing with KN046 when toxicity has improved to  $\leq$  Grade 1.

In case toxicity does not resolve to Grade 0-1 within 12 weeks after last infusion, trial treatment will be discontinued. With the agreement between investigator and Sponsor Medical Monitor, subjects with a laboratory adverse event at Grade 2 after 12 weeks may continue treatment only if asymptomatic and controlled, for example, hypothyroidism or Type 1 diabetes controlled by replacement treatments.

Subjects who require corticosteroids to manage drug-related adverse events must be at an equivalent dose of  $\leq 10$  mg per day of prednisone to resume dosing with KN046. In case of an inability to reduce the corticosteroid dose for managing a drug-related adverse event to the equivalent of  $\leq 10$  mg prednisone per day within 12 weeks of last KN046 dose, patient will go off treatment.

For a subject who experiences a recurrence of the same serious adverse event at the same grade or greater after rechallenge of KN046, study medication will be discontinued.

In addition, if any of below drug-related adverse events occur, KN046 treatment will be permanently discontinued:

- $\geq$  Grade 3 immune related pneumonitis;
- Recurrence of  $\geq$  Grade 2 immune related pneumonitis lasting  $\geq$  4 weeks after appropriate medical interventions;
- $\geq$  Grade 2 immune related CNS toxicities lasting  $\geq$  4 weeks after appropriate medical interventions;
- $\geq$  Grade 3 immune related colitis;
- $\geq$  Grade 3 uveitis or optic neuritis;
- $\geq$  Grade 3 immune related hepatitis with ALT/AST  $> 8 \times$  ULN OR TBIL  $> 3 \times$  ULN;
- $\geq$  Grade 3 immune related nephritis or renal dysfunction.
- $\geq$  Grade 2 myocarditis
- $\geq$  Grade 2 myositis

**Table 7-1** *Guideline on KN046 dose modification*

Toxicity	Grade	Withheld treatment	Resume treatment	Dose / schedule for resuming treatment	Discontinuation of treatment
Hematological toxicity	1, 2	No	Not applicable	Not applicable	Not applicable
	3 (except for isolate event of grade 3 neutropenia)	Yes			

Toxicity	Grade	Withheld treatment	Resume treatment	Dose / schedule for resuming treatment	Discontinuation of treatment
	4	Yes	Toxicity resolves to $\leq$ Grade 1 or baseline within 12 weeks of last KN046 dose	Resume at planned dose and increase the dose interval by 1 week at each occurrence	Permanent discontinuation if toxicity does not resolve to $\leq$ Grade 1 or baseline within 12 weeks of last KN046 infusion
Non-hematological toxicity with the exception for alopecia of any Grade and Grade 2 fatigue which will be treated as Grade 1 adverse reaction (with the exception of those reported in 7.3)	1	No	Not applicable	Not applicable	Not applicable
	2	Yes	Toxicity resolves to $\leq$ Grade 1 or baseline within 4 weeks of last KN046 dose	Resume at planned dose and dose interval	Permanent discontinuation if toxicity does not resolve to $\leq$ Grade 1 or baseline within 12 weeks of last KN046 infusion
			Toxicity resolves to $\leq$ Grade 1 or baseline beyond 4 weeks and within 12 weeks of last KN046 dose	Resume at planned dose and increase the dose interval by 1 week at each occurrence	
	3, 4	Yes	Toxicity resolves to $\leq$ Grade 1 or baseline within 12 weeks of last KN046 dose	Resume at planned dose and increase the dose interval by 1 week at each occurrence	Permanent discontinuation if toxicity does not resolve to $\leq$ Grade 1 or baseline within 12 weeks of last KN046 infusion; Permanent discontinuation should also be considered for any life-threatening or severe adverse reactions

Note: if increased Grade 3 or 4 CPK occurs, myocardial enzymes (CPK, CK, Tn1, TnT) should also be measured. KN046 will be permanently discontinued in case of elevation on treatment-related myocardial enzymes
					

Infusion related reactions, hypersensitivity reactions, and immune related adverse event should be handled according to the guidelines provided in Sections 7.5.1 and Appendix A, respectively.

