In Phase I data of KN046-CHN-001, the most frequently observed TRAEs was rash reported in 30 subjects (34.1%), followed by pruritus in 28 subjects (31.8%), alanine aminotransferase increased (ALT) in 17 subjects (19.3%), fatigue in 15 subjects (17.0%), infusion related reaction in 15 subjects (17.0%), aspartate aminotransferase (AST) increased in 12 subjects (13.6%), pyrexia in 11 subjects (12.5%) and arthralgia in 9 subjects (10.2%). 9 of the 88 subjects (10.2%) experienced at least one  $\geq$ Grade 3 TRAEs. Similar to the results of the KN046-AUS-001 trial, neither the treatment-related adverse events nor the irAEs in the dose escalation study of the KN046-CHN-001 trial were found to occur in a dose-dependent manner.

Management of irAEs include withholding KN046 until resolution of toxicity to Grade 1 or less. If toxicity is Grade 3 or more, steroids may be used. Further details for management can be found in Section Appendix A.

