#### **7.5. Special precautions**

As a routine precaution, subjects enrolled in this study must be observed for 2 hours after the completion of infusion of KN046 in an area with resuscitation equipment and emergency agents. At all times during study drug administration, immediate emergency treatment of an infusion-related reaction or a severe hypersensitivity reaction according to institutional standards must be assured, for instance, dexamethasone 10 mg and epinephrine in a 1:1000 dilution or equivalents should always be available along with equipment for assisted ventilation.

Infusion of KN046 will be stopped in case of  $\geq$ Grade 3 hypersensitivity or anaphylactic reaction. The treatment recommendations for infusion-related reactions, severe hypersensitivity reactions according to the NCI are outlined in Sections 7.5.1. All infusion-related reactions occurring during the infusion of KN046 or within 2 hours after completion of the administration of KN046 should be reported as AE of interest (See Section 13).

Investigators should monitor subjects closely for potential irAE, which may manifest at the earliest after the first dose of treatment. Such events may consist of autoimmune hepatitis, diarrhea and colitis, arthritis, persistent rash, glomerulonephritis, cardiomyopathy or inflammatory eye conditions etc. Details for irAE management please refer to Section Appendix A.

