**Table 16-5 Management of immune related skin toxicity**

CTCAE v5.0 Grade	KN046 Dosing Management	Action and Guidelines	Diagnostic Consideration
Grade 1-2 
 
• Skin rash, with or without symptoms, <30% body surface area (BSA)
 
	
 
• No change in KN046 dose
 
	
 
• Symptomatic treatment 
 
• Topical corticosteroids, eg betamethasone 0.1% cream or hydrocortisone 1%)
 
• Urea-containing creams in combination with oral antipruritics (eg, diphenhydramine HCl or hydroxyzine HCl)
 
 
 
• At investigator's discretion, treatment with oral steroids for Grade 2 events
 
• Treat as Grade 3 skin toxicity if Grade 2 skin toxicity accompanies apparent clinical signs and symptoms
 
	All attempts should be made to rule out other causes such as metastatic disease, infection or allergic dermatitis
Grade 3 
 
• Rash covers >30% BSA or Grade 2 with substantial symptoms
 
	
 
• Withhold KN046 treatment
 
	
 
• Dermatology consultation. Consider biopsy to confirm diagnosis
 
• Recommend oral steroids treatment, starting with prednisone 1 mg/kg/day or equivalent. When
 
	

		
symptoms improve to Grade 1 or less, steroid taper should be started and continued over no less than 4 weeks
	
Grade 4 

• Skin sloughing >30% BSA with associated symptoms (eg, erythema, purpura, epidermal detachment)

	

• Discontinue KN046

	

• Dermatology consultation. Consider biopsy and clinical dermatology photograph

• Initiate steroids at methylprednisolone 1~2 mg/kg/day or equivalent. When symptoms improve to Grade 1 or less, steroid taper should be started and continued over no less than 4 weeks

	

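### Section 7.3, Table 7-1 and Appendix A give inconsistent triggers for withholding and permanently stopping KN046, and no sentence says which prevails

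*Combined protocol and SAP*

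**What the plan says.** Section 7.3 contains three sets of instructions and refers to a fourth.

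- **Prose.** KN046 is withheld for drug-related toxicity of at least "Grade 3 drug-related toxicity, including laboratory abnormalities with the exception of laboratory abnormalities that are not clinically significant". Dosing may resume once toxicity is Grade 1 or less, and treatment ends if that takes more than 12 weeks from the last infusion. Recurrence of the same serious adverse event at the same or a higher grade after rechallenge also ends treatment.
- **Mandatory list.** An added list of drug-related events ends treatment permanently. It includes immune-related hepatitis of Grade 3 or higher with ALT/AST above 8 x ULN or bilirubin above 3 x ULN, and a recurrence of pneumonitis of Grade 2 or higher that lasts at least 4 weeks after appropriate intervention.
- **Table 7-1.** Grade 2 non-hematological toxicity is withheld, with a row exception worded "with the exception of those reported in 7.3". Grade 3 hematological toxicity is withheld "except for isolate event of grade 3 neutropenia". The Grade 3-4 non-hematological row allows resumption within 12 weeks but adds: "Permanent discontinuation should also be considered for any life-threatening or severe adverse reactions".
- **Referral.** Below the table, infusion reactions, hypersensitivity and "immune related adverse event should be handled according to the guidelines provided in Sections 7.5.1 and Appendix A, respectively". Section 7.5 repeats this: "Details for irAE management please refer to Section Appendix A".

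Appendix A stops KN046 for hepatitis with ALT or AST above 5 x ULN, whatever the bilirubin. For Grade 2 pneumonitis it stops for a second episode of Grade 2 or higher on rechallenge and, as a separate trigger, for an episode lasting at least 4 weeks.

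**The concern.** For the same event, one operative passage withholds KN046 and another does not name it, or one passage ends treatment and another leaves a route back to dosing. These rules decide whether a patient is re-exposed after toxicity, so the first stake is patient safety. Phase I shows that the question is practical: KN046-AUS-001 recorded a Grade 3 hepatic dose-limiting toxicity without bilirubin increase at 5 mg/kg Q2W, the dose used here (Section 2.3.2.1.1). Its ALT/AST value, and whether it counted as immune-related, are not given there, so it cannot be placed in the disputed window.

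The second stake is the exposure summary. Section 12.4.2 plans to report dose intensity, relative dose intensity and the number of dose delays. All three depend on which passage a treating physician follows.

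**Working it through.** The plan states no figure to reproduce. The check sets the triggers side by side and then asks what the phase I tables say about frequency.

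**Withholding, events that are not immune-related**

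| Event | 7.3 prose | Table 7-1 |
|---|---|---|
| Grade 2 non-hematological | not named | withhold |
| Isolated Grade 3 neutropenia | within Grade 3 or higher unless judged not clinically significant | excepted |

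The row exception "with the exception of those reported in 7.3" does not settle the first line. It sits inside 7.3, names no event, and could mean the mandatory list or everything in the section.

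**Permanent stop, immune-related hepatitis**

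| ALT/AST | Bilirubin | 7.3 list | Appendix A |
|---|---|---|---|
| >5 to 8 x ULN | ≤3 x ULN | not listed | stop |
| >5 to 8 x ULN | >3 x ULN | stop | stop |
| >8 x ULN | any | stop | stop |

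Only the first line differs. There, the general rule in 7.3 says dosing may resume after recovery. Whether the Grade 3-4 row of Table 7-1 also applies is unclear, because of its exception and the referral below the table.

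**Permanent stop, Grade 2 pneumonitis**

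| Course | Section 7.3 | Appendix A |
|---|---|---|
| First episode, ≥4 weeks | not listed | stop |
| Second episode, <4 weeks, serious recurrence at same or higher grade | stop (serious-recurrence rule) | stop |
| Second episode, <4 weeks, not serious | not listed | stop |
| Second episode, ≥4 weeks | stop | stop |

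**Lesser instances.** Appendix A stops for Grade 2 nephritis that persists beyond 7 days or worsens; the 7.3 list starts at Grade 3. Appendix A appears to stop for Grade 1 myocarditis; the 7.3 list starts at Grade 2. The myocarditis cell may be merged across grades, and the enzyme note under Table 7-1 covers part of this case.

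**Frequency of the hepatitis window at 5 mg/kg Q2W.** Inputs are the Grade 3 or higher columns of Table 2-4 (AUS, N = 30) and Table 2-10 (CHN, N = 45).

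- AUS: 1 subject with ALT increased and 1 with hepatic function abnormal. Overlap is not stated, so 1 or 2 subjects.
- CHN: 0 subjects.
- Pooled: 1/(30 + 45) = 1/75 = 1.3% (exact 95% CI 0.03% to 7.2%), or 2/75 = 2.7% (0.3% to 9.3%).
- The share with ALT/AST above 5 to 8 x ULN and bilirubin ≤3 x ULN is not reported and may be anything from 0 to 1. The window therefore holds 0 to 2 of 75.

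Two cautions apply: Table 2-4 shows no term with fewer than 2 subjects in total, and the trials graded with different CTCAE versions (4.03 and 5.0).

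**Frequency of the Grade 2 withholding conflict.** From Tables 2-3 and 2-9 at 5 mg/kg Q2W, related rash was 3 + 13 = 16 of 75 (21.3%) and related pruritus 3 + 14 = 17 of 75 (22.7%), none Grade 3 or higher. Grades 1 and 2 are not separated, so the Grade 2 counts are 0 to 16 and 0 to 17. How many were not immune-related is also unknown.

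**Pneumonitis.** Table 2-10 lists 2 immune-related cases, both at 3 mg/kg Q2W, and none at 5 mg/kg Q2W. They give no usable rate for this trial's dose.

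**The case against.** The strongest reply is that nothing here is a contradiction in logic. The 7.3 list is introduced as an addition and states sufficient reasons to stop, not the only ones. Appendix A is the stricter text in each stopping example, and Sections 2.4.1.1, 7.3 and 7.5 all send immune-related events to it. A site could comply with both by following Appendix A. On withholding, the prose is silent on Grade 2 rather than permissive, so the table may be read as completing it. The prose exception for laboratory findings of no clinical significance may overlap with the neutropenia exception.

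Much of this stands, and it limits the point. It does not remove it. If Appendix A governs, the 8 x ULN limit and the combined recurrence-and-duration condition in 7.3 have no effect, yet they are written as mandatory for named immune-related events. Appendix A describes itself as general principles, and no sentence gives it precedence. The referral also does nothing for Grade 2 events that are not immune-related.

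Three stronger readings are tempting but unsupported.

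- A reader might infer that Section 2.4.1.1 ("Management of irAEs include withholding KN046 until resolution of toxicity to Grade 1 or less") contradicts Appendix A, which has "No change in KN046 dose" for Grade 1-2 rash. That section is a summary and itself sends the reader to Appendix A for details.
- A reader might infer that 7.3 lets every second Grade 2 pneumonitis be re-dosed. Its serious-recurrence rule narrows the gap to non-serious recurrences under 4 weeks.
- A reader might subtract immune-related from related skin events to count those governed by Table 7-1. That assumes one is a subset of the other. In AUS at 5 mg/kg, increased transaminases appear as immune-related in 3 subjects (Table 2-4) but as related in 2 (Table 2-3).

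**Conclusion.** The inconsistency is real and the text is wrong as written. Three differences matter:

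- the Grade 2 withholding trigger within 7.3 for events that are not immune-related;
- hepatitis with ALT/AST above 5 to 8 x ULN and bilirubin ≤3 x ULN;
- Grade 2 pneumonitis, chiefly a first episode lasting at least 4 weeks.

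The last two are unresolved overlaps rather than strict contradictions.

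The number of patients affected cannot be derived from the documents, so the case rests on conflicting safety instructions and not on frequency. A reader might infer that the efficacy result is compromised. The documents do not support that: the response rate analysis and the Simon design do not depend on these rules as specified. The effects are on patient safety and on the dose-delay and dose-intensity summaries. The conclusion assumes that the extracted tables show the actions against the correct grades; the one cell in doubt, Grade 1 myocarditis, is not relied on.

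**What to change.** Reconcile the 7.3 prose, the 7.3 list, Table 7-1 and Appendix A so that each toxicity and grade has one action. Begin with Grade 2 non-hematological toxicity, hepatitis and pneumonitis, then isolated Grade 3 neutropenia, persistent or worsening Grade 2 nephritis and Grade 1 myocarditis. Name the events that the Table 7-1 row excepts. Add one sentence stating how the 7.3 list relates to Appendix A for immune-related events. The clinical team decides the thresholds; none is proposed here.

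The cost is amendment wording and IRB approval, with no new procedures, visits or patients.
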